**Could miRNAs be used as markers for distinguishing
undescended testicles from retractile testicles**

No NCT number assigned yet

31.03.2022

1. Study protocol

1.1.Sample size

This study is designed as a prospective controlled trial to compare miRNA changes across UDT, RT, and normal control groups. The sample size was determined via G*Power 3.1.9.6. A one-way ANOVA power analysis for miR-34c, which compared three groups, utilized an effect size ($f=1.2955357$) from a previous study [10]. To achieve 99% power and a 1% error rate, a total sample size of 24 was needed. To increase confidence, the study ultimately enrolled 30 patients, who were divided into three groups of 10.

1.2.Patient population

Initially, 10 boys with undescended testicles (UDTs), 10 with retractile testicles (RTs), and 10 healthy volunteers (controls) from our urology clinic (dates between March 2022 and March 2023) were enrolled. However, one RT patient and one control patient were excluded because of parental refusal for blood sampling. Only palpable (unilateral or bilateral) UDT cases were included, excluding nonpalpable types. To ensure accurate RT diagnosis, initial physician examinations were performed in three positions (supine, semisupine, standing), followed by a 1-month parental examination (twice daily). Only RT patients whose testicles spent $>50\%$ of their time in the scrotum were included. The exclusion criteria also included prior inguinal/scrotal surgery, defective datasets, or unsuitable serum samples.

1.3.Collection of patient data and control samples

Detailed patient histories, physical examinations, and routine biochemical tests were performed. UDT blood samples were collected presurgery to prevent misinterpretation. Blood from all the groups was collected in 5 mL biochemistry tubes and centrifuged at 3000 rpm for 10 minutes. The resulting

particle-free serum was transferred to 1.5 mL tubes and stored at -80°C until analysis.

1.4. Validation of the expression levels of miR-210, miR-449a and miR-34c via real-time PCR

Serum samples from the urology clinic were subjected to RNA isolation via the Quick-cfRNA™ Serum & Plasma Kit (Zymo Research). The extracted miRNA was reverse transcribed into cDNA via the miRNA All-In-One cDNA Synthesis Kit (ABMGood). cDNA quality and quantity were assessed spectrophotometrically with a BioSpec-nano instrument (Shimadzu) before real-time PCR. miRNA expression analysis was performed via a Rotor Gene Q (Qiagen) instrument. The levels of miR-210, miR-449a, and miR-34c were quantified with ready-to-use primers and BlasTaq™ 2X qPCR MasterMix (ABMGood).

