1.5. Statistical analysis

Data normality was assessed via the Shapiro–Wilk test, and variance equality was assessed via Levene's test. Descriptive statistics are presented as the means \pm SDs for parametric data and medians (IQRs) and means (ranks) for nonparametric data. For group comparisons, one-way ANOVA was used for parametric data, and the Kruskal–Wallis test was used for nonparametric data, followed by the Dunn–Bonferroni correction for post hoc multiple comparisons. Spearman's rank correlation coefficient was used to analyse correlations. Statistical significance was set at $p < 0.05$.

miRNA expression was quantified via qRT–PCR via C_t (crossing point) values and normalized to RNU6B_13. Relative miRNA expression levels were compared among all groups via the $2^{-\Delta C_t}$ method and calculated as 2^{C_t}

$(\text{target gene}) - C_t (\text{reference gene})$. All the statistical analyses were performed via IBM SPSS v28 (IBM Inc., Chicago, IL, USA).

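### The title asks whether a miRNA can tell UDT from RT, but section 1.5 plans no estimate, with a confidence interval, of how well any miRNA separates them

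*Combined protocol and SAP*

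**What the plan says.** The title poses a two-group question: "Could miRNAs be used as markers for distinguishing" UDT from RT. Section 1.1 words the purpose more narrowly, as a design "to compare miRNA changes across UDT, RT, and normal control groups", and sizes the study on a three-group ANOVA for miR-34c: "To achieve 99% power and a 1% error rate, a total sample size of 24 was needed".

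Section 1.2 reports that 10 boys per group were enrolled and that "one RT patient and one control patient were excluded because of parental refusal for blood sampling". This leaves 10 UDT, 9 RT and 9 controls, 28 in all.

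Section 1.5 sends parametric data to one-way ANOVA and nonparametric data to Kruskal–Wallis, "followed by the Dunn–Bonferroni correction for post hoc multiple comparisons". Descriptives are means ± SDs for parametric data and "medians (IQRs) and means (ranks) for nonparametric data". It adds that "Spearman's rank correlation coefficient was used to analyse correlations", without naming the variables, and sets significance at p<0.05. No section mentions a ROC curve, AUC, sensitivity, specificity, cut-off, or a confidence interval for any contrast.

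**The concern.** Whether a marker distinguishes two conditions is a question about overlap: how often a UDT boy's value lies on the expected side of an RT boy's value. A group test asks only whether the distributions differ. Followed as written, section 1.5 yields a p value and group summaries for UDT versus RT, and a reader could take a significant p value as an affirmative answer to the title. In groups this small, significance alone does not show whether the separation is weak or strong. What is at stake is a claim of marker usefulness with no stated strength or precision behind it.

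**Working it through.** **1. The plan's own figure.** For a one-way ANOVA with three groups, f = 1.2955357 and noncentrality N·f², power at the 1% level is 0.988 for N = 21 and 0.997 for N = 24. The stated 24 is the smallest equal-group total that reaches 99%, so the arithmetic is sound. It concerns the three-group omnibus test, however. Under equal-variance normality the same f fits very different UDT–RT separations:

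- Only the controls differ: UDT–RT AUC = 0.50.
- Means equally spaced, UDT and RT adjacent: spacing = f/√(2/3) = 1.587 SD, so AUC = Φ(1.587/√2) = 0.87.
- Means equally spaced, UDT and RT at the extremes: 3.173 SD, so AUC = Φ(3.173/√2) = 0.99.

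The sample size therefore says nothing definite about the title question.

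**2. What a significant UDT–RT result implies.** The group sizes are 10 and 9 (section 1.2), giving 10 × 9 = 90 pairs and 92,378 possible rank arrangements. The observed AUC is 1 − U/90. The two-sided exact p values are:

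| U | Observed AUC | Exact p |
|---|---|---|
| 21 | 0.767 | 2 × 2470/92378 = 0.0535 |
| 20 | 0.778 | 2 × 2008/92378 = 0.0435 |
| 16 | 0.822 | 2 × 795/92378 = 0.0172 |
| 15 | 0.833 | 2 × 613/92378 = 0.0133 |

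The thresholds are thus AUC 0.778 at 0.05 and 0.833 at 0.05/3 = 0.0167 (three pairwise comparisons). This two-group test is not in the plan; it stands in for the planned pairwise step.

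**3. The uncertainty at those thresholds.** The Newcombe score-type limits are the values θ that solve |AUC − θ| = 1.96·√V(θ), where V(θ) = θ(1−θ)[1 + 8.5·((1−θ)/(2−θ) + θ/(1+θ))]/90 and 8.5 = (10+9)/2 − 1.

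- AUC 0.778: 0.511 to 0.915, width 0.404. Check of the lower limit: V(0.511) = 0.0185, and 1.96 × √0.0185 = 0.267 = 0.778 − 0.511.
- AUC 0.833: 0.570 to 0.945.

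**4. The Kruskal–Wallis route.** Dunn's test ranks all 28 boys. Its Bonferroni critical mean-rank difference for UDT versus RT is 2.394 × √[(28 × 29/12) × (1/10 + 1/9)] = 9.05. With C for controls, the difference itself equals 19·(AUC_UR − 0.5) + 9·(AUC_UC − AUC_RC). The second term involves the controls, so the UDT–RT result can move with their position while UDT–RT separation stays fixed. If controls rank exactly like RT, the threshold is 0.5 + 9.05/28 = 0.823. For the same reason, mean ranks over 28 boys do not determine the two-group AUC; nor do medians with IQRs.

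**5. The ANOVA route.** Here means ± SDs are reported, and under normality AUC ≈ Φ[(difference in means)/√(SD²_UDT + SD²_RT)]. A reader could reconstruct an approximate AUC, and with the group sizes an approximate interval. The plan does not call for either.

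**The case against.** The strongest reply is that the analysis matches the written aim. Section 1.1 speaks of comparing groups, the sample size follows from that, and the mismatch is with a title phrased as a question. This stands, and it is why rewording is a full alternative remedy. It does not help if the title and a marker conclusion are kept.

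A second reply is that an AUC would not settle the matter either, since an interval about 0.40 wide leaves much undecided. That is also true. The gain is that the uncertainty becomes visible.

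Three stronger readings are tempting, and the documents do not support them:

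- **That UDT and RT are never compared.** The Dunn–Bonferroni pairs include this one. What is absent is an estimate with an interval.
- **That the planned UDT–RT result is at the mercy of the controls.** If Dunn's test were applied to every dataset, normal data with a true AUC of 0.869 would give significance in about 71% of studies with controls like RT, but about 9% with controls wholly outside the UDT and RT values. Section 1.5, however, sends parametric data to ANOVA, and some 80 to 83% of such datasets would pass both preliminary checks. Routed that way, the contrast is about 80% against about 66 to 70%. This assumes Bonferroni t-tests with a pooled SD after ANOVA, because section 1.5 does not clearly name that step. Nothing in the documents suggests controls that extreme.
- **That the descriptives are useless for this purpose.** That is fair for medians, IQRs and mean ranks, but not for means ± SDs on the parametric route.

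**Conclusion.** The point holds as a gap between question and analysis. The planned tests are valid for the aim in section 1.1, and the sample-size calculation reproduces. No planned output directly states, with its uncertainty, how well any miRNA separates UDT from RT. At the edge of significance the data would be compatible with an AUC from about 0.51 to 0.92 (unadjusted) or 0.57 to 0.94 (at 0.05/3).

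These figures rest on 10 versus 9 evaluable boys, on untied values, and on a two-group rank test as a stand-in for the planned comparison. The documents give no AUC, so none is attributed to the trial. The dependence on controls is a secondary matter, confined to the Kruskal–Wallis route. This should be changed, but it does not invalidate the group comparison.

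**What to change.** Add to section 1.5, labelled exploratory because section 1.2 already reports enrolment and exclusions:

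- The ROC AUC for UDT versus RT for miR-34c first (the marker used for the sample size), then miR-210 and miR-449a, with all three reported.
- A 95% confidence interval for each from a method suited to small samples. A Newcombe score-type interval is one example and needs only the AUC and the two group sizes.
- The direction of each marker, stated in advance or reported as chosen from the data. With no true separation, choosing the direction afterwards gives a mean AUC of about 0.61 for one miRNA: 0.5 + 0.798 × √(20/1080) = 0.609.
- Any statement about marker usefulness based on the whole interval, not on the p value.

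Otherwise, limit the title and conclusion to group differences in miRNA levels.

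The first option costs a little analysis on data already collected, wide intervals (about 0.40 at an observed AUC of 0.778) and a more cautious conclusion. The second costs only wording, but gives up the marker claim.

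### The 99% power in 1.1 belongs to the three-group test on miR-34c; for UDT versus RT, the title question, section 1.5 names only Dunn–Bonferroni, which gives up power that a closed three-group procedure would keep

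*Combined protocol and SAP*

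**What the plan says.** The title asks "Could miRNAs be used as markers for distinguishing" undescended from retractile testicles, which is a two-group question. Section 1.1 declares a wider aim, "to compare miRNA changes across UDT, RT, and normal control groups", and sizes the study for it: "A one-way ANOVA power analysis for miR-34c, which compared three groups, utilized an effect size" of f=1.2955357 taken from an earlier study. The result is given as "To achieve 99% power and a 1% error rate, a total sample size of 24 was needed". Thirty boys were enrolled, 10 per group. Section 1.2 then reports that "one RT patient and one control patient were excluded because of parental refusal for blood sampling", which leaves 10 UDT, 9 RT and 9 controls.

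Section 1.4 covers three markers: "The levels of miR-210, miR-449a, and miR-34c were quantified with ready-to-use primers". Section 1.5 says that "one-way ANOVA was used for parametric data" and that "the Kruskal–Wallis test was used for nonparametric data, followed by the Dunn–Bonferroni correction for post hoc multiple comparisons", with significance at 0.05. Neither 1.1 nor 1.5 gives a UDT–RT difference, a power for that pair or a smallest detectable difference.

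**The concern.** An omnibus f summarises the spread of three means and does not say which groups differ. The three-group test can be significant because controls differ while UDT and RT are the same. A reader who takes the title as the question and the 99% as its power could read a non-significant UDT–RT result as strong evidence against the marker.

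The post hoc method adds to this. Dunn's test compares mean ranks computed over all three groups, with a standard error that also comes from all 28 ranks. If RT lies between UDT and controls, the UDT–RT rank gap is small relative to that standard error, however cleanly the two groups separate. Bonferroni then multiplies the p-value by 3. With exactly three groups, familywise error can be controlled without either cost.

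**Working it through.** **1. The plan's own figure.** Inputs from 1.1: k=3, f=1.2955357, alpha 0.01, target power 99%. Power = P(F′ > F crit), where F′ is noncentral F with 2 and N−3 df and λ = N·f².
- N=21: λ=35.2, power 98.8%
- N=24: λ=40.3, power 99.67%
- N=28: λ=47.0, power 99.95% (balanced approximation)

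So 24 is the smallest balanced total that reaches 99%, and the figure is right.

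**2. What f says about UDT versus RT.** Put UDT at 0, RT at xD and controls at D, in SD units. With equal weights f² = 2D²(1−x+x²)/9, so D = 3f/√(2(1−x+x²)) and the UDT–RT difference is d = xD.
- x=0: d=0
- x=0.5: D = f√6 = 3.17, d=1.59
- x=1: d=2.75
- UDT and RT as the two extremes with controls midway: d=3.17

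The same f therefore allows any UDT–RT difference from 0 to 3.17.

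**3. An exact case that needs no distribution.** Suppose UDT < RT < controls with no overlap (10/9/9). The UDT and RT mean ranks are 5.5 and 15. The Dunn standard error is √(28·29/12·(1/10+1/9)) = 3.78, so z = 9.5/3.78 = 2.51, p=0.012, and ×3 = 0.036. The exact Mann–Whitney p on the same boys, also ×3, is 6/C(19,9) = 6/92,378 = 0.000065.

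Now keep controls clear of both groups and let U of the 90 UDT–RT pairs be out of order. The mean-rank gap becomes 9.5 − U(1/10+1/9). The adjusted Dunn p is 0.049 at U=2 and 0.057 at U=3, so Dunn–Bonferroni tolerates only 2 discordant pairs of 90. An exact Mann–Whitney test at 0.05 tolerates 20 (attained level 4.35%).

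**4. Power under an assumed pattern.** The documents give no group means, so this is illustration: normal data with equal variances, f=1.2955 on the analysed scale, n=10/9/9, alpha 0.05. The rank-branch figures come from 100,000 simulated data sets per pattern, and every pairwise result required a significant omnibus test.

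| RT position from UDT (0) to control (1) | d | Dunn–Bonferroni | Closed Mann–Whitney |
|---|---|---|---|
| 0.2 | 0.60 | 1% | 21% |
| 0.4 | 1.26 | 13% | 69% |
| 0.5 | 1.59 | 33% | 87% |
| 0.6 | 1.89 | 60% | 96% |
| 0.8 | 2.40 | 93% | >99% |
| 1.0 | 2.75 | 99% | >99% |

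The first row mostly reflects a small effect. If UDT and RT are the extremes, Dunn–Bonferroni power is about 100%.

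For the ANOVA branch use noncentral t with 25 df and noncentrality d/√(1/10+1/9). With RT midway, a Bonferroni pooled t test (alpha 0.05/3; 1.5 does not name it) gives 80.5%. The closed pooled t test gives 91.3%, and simulation agrees.

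**5. Why the closed procedure is valid.** If all three groups are equal, a pairwise claim requires a false omnibus rejection, at most 5%. If exactly two are equal, only one pairwise null is true, and it is tested at 5%. No other case has a true null. With only controls shifted, the simulated UDT–RT error is about 4.4% for closed Mann–Whitney and about 5% for closed pooled t.

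**The case against.** **The plan does what 1.1 says.** The declared aim is a three-group comparison, the ANOVA power is correctly labelled, and 24 is correct. This stands. A reader might infer that the sample size is wrong or that the trial is underpowered for UDT versus RT. The documents support neither: the pairwise power is unstated, not shown to be low, and it is about 99% if RT resembles controls.

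**The 33% scores normal data in the rank branch.** Section 1.5 would send most such data to ANOVA. In a rerun of the midway case with an assumed Shapiro–Wilk screen per group at 0.05, only 14% of data sets went to Kruskal–Wallis. With a Bonferroni pooled t test standing in for the unnamed ANOVA post hoc test, overall power was about 74%, against 91% for the closed procedure. This stands too. The 33% versus 87% contrast applies only if the data really go to Kruskal–Wallis, and it is not the expected loss for the plan as a whole.

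**Joint ranking cannot be named as the main cause.** Unadjusted Dunn gives 66% in the midway case. Removing the factor of 3 first gains 33 points and ranking the pair alone then gains 21; in the other order the split changes. Only the combined effect should be quoted.

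**Dunn–Bonferroni is a recognised method, and the text is in the past tense.** Both are true. The proposal is an improvement in power, not the correction of an invalid test. If results have been seen, a more liberal procedure cannot be presented as prespecified.

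**Sizing at 1% and testing at 5%** is conservative for the omnibus test. It needs stating but does no harm.

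**Conclusion.** The point holds in a limited form. The 99% is correct omnibus power for miR-34c at alpha 0.01 and says nothing definite about UDT versus RT. The missing pairwise power is a missing detail. The substantive gain is in 1.5, where a closed procedure does better for the title comparison at no cost in boys or assays. In the midway illustration the gain is about 10 points after ANOVA and 54 points after Kruskal–Wallis (87 − 33). It shrinks to almost nothing as RT approaches controls.

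These sizes rest on normality, equal variances, f applying on the analysed scale, and an assumed position for RT. The documents settle neither that position, nor the branch, nor the scale on which f was estimated. The exact result in step 3 needs no distributional assumption, but it does assume that controls lie beyond both other groups.

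**What to change.** **In 1.5**, replace Dunn–Bonferroni with the closed three-group procedure: omnibus test at 0.05 and, if significant, each pair at 0.05, by Mann–Whitney after Kruskal–Wallis or by pooled t test after ANOVA. State that this controls familywise error within one miRNA only, since three are measured. If any results have been examined, label this change as post hoc, and likewise any naming of miR-34c as primary, and report the Dunn–Bonferroni result beside it.

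**In 1.1**, say that 99% is omnibus power for miR-34c at alpha 0.01, whereas 1.5 tests at 0.05. If a detectable UDT–RT difference is added, compute it for the gated test actually used. Plain two-group calculations for 10 versus 9 give 80% at d=1.37 and 90% at d=1.58 (t test), or d=1.44 and 1.67 (exact Mann–Whitney). These should not be inserted, because the omnibus gate changes them. By simulation, depending on where controls lie, the closed pooled t test gives about 70–82% at d=1.37 and 83–91% at d=1.58. Closed Mann–Whitney gives about 70–80% at d=1.44 and 83–90% at d=1.67.

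**Cost:** wording in two sections and a rerun of the pairwise tests. The UDT–RT error rate when only controls differ rises from under 0.1% (Dunn–Bonferroni) to about 4.4% (closed Mann–Whitney), or from about 1.7% (Bonferroni pooled t) to about 5% (closed pooled t). That uses the 5% allowance that 1.5 already sets. The closed result may have to carry a post hoc label.

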1.5. Statistical analysis

Data normality was assessed via the Shapiro–Wilk test, and variance equality was assessed via Levene's test. Descriptive statistics are presented as the means \pm SDs for parametric data and medians (IQRs) and means (ranks) for nonparametric data. For group comparisons, one-way ANOVA was used for parametric data, and the Kruskal–Wallis test was used for nonparametric data, followed by the Dunn–Bonferroni correction for post hoc multiple comparisons. Spearman's rank correlation coefficient was used to analyse correlations. Statistical significance was set at $p < 0.05$.

miRNA expression was quantified via qRT–PCR via C_t (crossing point) values and normalized to RNU6B_13. Relative miRNA expression levels were compared among all groups via the $2^{-\Delta C_t}$ method and calculated as 2^{C_t}

$(\text{target gene}) - C_t (\text{reference gene})$. All the statistical analyses were performed via IBM SPSS v28 (IBM Inc., Chicago, IL, USA).
